11.2 Primary Efficacy Analysis

11.2.1 Primary Efficacy Endpoint

The primary endpoint will be the percentage of responders, defined as subjects meeting the following two conditions:

- MBL volume < 80 mL at the Final Month (the last 28 days prior to and including the Reference Day), and
- 50% or greater reduction in MBL volume from Baseline to the Final Month (the last 28 days prior to and including the Reference Day)

Subjects who prematurely discontinue study drug due to "lack of efficacy," "requires surgery or invasive intervention for treatment of uterine fibroids," or adverse events will be considered as non-responders. Only primary discontinuation reason is considered.

Baseline MBL volume is defined in Section 7.1.

Final Month is defined as in Section 7.2. If a subject has less than or equal to 28 days of treatment prior to and including the Reference Day, then the Final Month will be the interval between Day 2 to the Reference Day. The AH data on Day 1 will be included in the Baseline MBL volume calculation (provided it is part of a qualifying menstrual cycle) and will not be included in post-baseline MBL volume calculation.

[figure not shown]

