urine pregnancy test cannot be performed at the study site or other medical facility within 24 hours prior to an SIS and/or endometrial biopsy. The subject must self-administer and report a negative urine pregnancy test result to the site within 24 hours prior to undergoing these procedures.

A positive urine pregnancy test result must be confirmed with a quantitative serum pregnancy test. The subject should temporarily discontinue study drug administration while waiting for the results of the serum pregnancy test. If a serum pregnancy test result is positive at any time during the Treatment Period, the site will immediately inform the subject to discontinue study drug (Section 6.1.6). If a subject is confirmed as pregnant, the subject will be prematurely discontinued from the study.

An ultrasound examination will be performed during the first trimester of pregnancy to assess the gestational age and estimated date of delivery if the subject becomes pregnant during the Treatment or Post-Treatment Follow-Up Periods of the study. Refer to Section 6.1.6 for instructions on reporting of a pregnancy to the Sponsor and the required follow-up on the subject/fetus and live infant births.

5.3 Efficacy, Pharmacokinetic, Pharmacodynamic, Pharmacogenetic and Safety Assessments/Variables

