5.4 Removal of Subjects from Therapy or Assessment

Each subject has the right to withdraw from the study at any time. In addition, the Investigator may discontinue a subject from the study at any time if the Investigator considers it necessary for any reason, including the occurrence of an adverse event or noncompliance with the protocol. Subjects who withdraw from the study will not be replaced unless it is mutually agreed upon, in writing, by the Investigator and AbbVie. Each subject will be withdrawn from the study if any of the following occur:

- The subject decides to withdraw consent for any reason.
- The investigator believes it is in the best interest of the subject.
- Clinically significant deterioration of the subject's medical status as determined by the investigator.
- The subject requires surgical intervention for treatment of uterine fibroids and menstrual bleeding or other procedures including hysterectomy, myomectomy, uterine artery embolization, high intensity focused ultrasound (HIFU), endometrial ablation, dilation and curettage (D&C), etc. during the Treatment Period. In the post treatment period these procedures do not warrant withdrawal if performed during the Post-Treatment Period unless a hysterectomy with bilateral salpingo-oophorectomy (BSO) is performed and the Subject does not plan to use Hormone Replacement Therapy within 1 month of the surgery date.
- The subject becomes pregnant.

- The subject has (SGPT/ALAT) or SGOT/ASAT elevation > 5 times the upper limit of normal confirmed upon repeat during the Treatment Period.
- The subject's legally acceptable representative decides to withdraw consent for any reason.
- Heavy menstrual bleeding during the Treatment Period that requires a blood transfusion at any time after having taken 28 days of study drug. If a subject has a blood transfusion during the Post-Treatment Period, the AbbVie TA MD should be contacted to determine if the subject can remain in the study.
- Any other medical reason that AbbVie or the study investigator deems appropriate.

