5.4.1 Discontinuation of Individual Subjects

In the event that a subject withdraws or is prematurely discontinued from study drug treatment, the subject should complete the Treatment Period Premature Discontinuation Visit as soon as possible (preferably within 2 - 7 days of last dose of study drug, if possible) and undergo study procedures as outlined in Appendix C. Subjects who prematurely discontinue during the Treatment Period are expected to enter the 12-Month Post-Treatment Follow-Up Period.

In the event that a subject withdraws or is prematurely discontinued during the Post-Treatment Follow-Up period, the subject should complete the Post-Treatment Premature Discontinuation Visit as soon as possible and undergo study procedures as outlined in Appendix C. These procedures should not interfere with the initiation of any new treatments or therapeutic modalities the Investigator determines are necessary to treat the subject's condition. The reason(s) for the discontinuation from the study will be recorded in the eCRFs.

All used and unused study drug containers will be returned to the study site.

If a subject becomes pregnant during the Treatment or Post-Treatment Follow-Up Periods, no additional study procedures, except an ultrasound will be conducted. Refer to

Section 6.1.6 for instructions on reporting of a pregnancy to the Sponsor and the required follow-up on the subject/fetus and live births.

Subjects who prematurely discontinue from treatment and enter Post-Treatment Follow-Up and received study drug for < 3 months or the procedure was performed in the past two months are not required to undergo the following procedures during the Post-Treatment Period, unless requested by the AbbVie TA MD or based on clinical judgment:

Post-Treatment Period Month 3:

- TAU/TVU
- MRI

Post-Treatment Period Month 6:

- TAU/TVU
- DXA (unless the premature discontinuation was related to BMD decrease or the occurrence of a fracture)

If a subject is discontinued from the study with an ongoing adverse event or an unresolved laboratory result that is clinically significant (as determined by the Investigator), the Investigator will attempt to provide follow-up until a satisfactory clinical resolution of the laboratory result or adverse event is achieved.

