6.1.6 Pregnancy

Pregnancy in a study subject must be reported to AbbVie within 1 working day of the site becoming aware of the pregnancy. Subjects who become pregnant during the Treatment or Post-Treatment Follow-Up Periods of the study must be discontinued (Section 5.4 and Section 5.4.1). A positive urine pregnancy test result must be confirmed with a serum pregnancy test. If a serum pregnancy test result is positive at any time during the Treatment Period of the study, the site will immediately inform the subject to discontinue study drug. Information regarding a pregnancy occurrence in a study subject and the outcome of the pregnancy will be collected for any study subject with a positive serum pregnancy test from the signing of the informed consent (i.e., washout [if applicable]) or screening) through the Post-Treatment Follow-Up Period. The site will report a positive pregnancy test to the Sponsor, will follow the course of the subject's pregnancy, and report to the Sponsor on the health of the subject and fetus at each trimester and at the first post-delivery pediatrician visit.

If the subject becomes pregnant during the Treatment or Post-Treatment Follow-Up Periods of the study, an ultrasound examination will be performed as early as possible during the first trimester of pregnancy to assess the conception date and document an intrauterine pregnancy. The following information on the outcome of the pregnancy that occurred after signing of the informed consent, regardless of when the subject became pregnant (i.e., either during the Washout, Screening, Treatment or Post-Treatment Follow-Up Periods) should be collected: fetal outcome (e.g., spontaneous or elective abortion, live infant or still birth), date of delivery, birth weight, birth length, gender, birth

defects, congenital anomaly and medically significant complications during pregnancy or labor or delivery. For live infant births, information on the health of the infant will be collected 6 to 12 months after delivery.

Pregnancy in a study subject is not considered an adverse event. However, the medical outcome of an elective or spontaneous abortion, stillbirth or congenital anomaly is considered a serious adverse event and must be reported to AbbVie within 24 hours of the site becoming aware of the event.

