7.2 Definitions of Final Month and Final Visit

Final Month is defined as the last 28 days prior to and including the Reference Day, which is defined as the last visit date in the treatment period (last treatment visit date) or the last dose date if there is evaluable Alkaline Hematin (AH) data after the last treatment visit date and prior to or on the last dose date.

Final Visit is defined as the last non-missing assessment during the Treatment Period.

Post-Treatment Final Visit is defined as the last non-missing assessment during the Post-Treatment Follow-up Period.

7.3 Definition of Study Days (Days Relative to the First Dose of Study Drug) and Study End Days (Days Relative to the Last Dose of Study Drug)

For randomized subjects who received at least one dose of study drug, the study day is defined as the number of days since (positive values) or prior to (negative values) the first study drug dose. The day of the first study drug dose is defined as Study Day 1 while the last day prior to the first dose of study drug is defined as Study Day -1. There is no Study Day 0. Study end days are calculated based on the number of days relative to the last dose of study drug. The first day following the last dose of study drug is defined as Study End Day 1.

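### Discontinuation for pregnancy falls outside the non-responder rule, so absence of menses due to pregnancy can be scored as response, suppression of bleeding or amenorrhea

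*SAP*

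**What the plan says.** **Non-responder rule.** SAP 11.2.1 overrides measured MBL for three reasons for stopping study drug: lack of efficacy, surgery or invasive intervention for fibroids, and adverse events ("or adverse events will be considered as non-responders"). It adds: "Only primary discontinuation reason is considered".

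**Status of pregnancy.** Protocol 6.1.6: "Pregnancy in a study subject is not considered an adverse event". Protocol 5.2.4: "If a subject is confirmed as pregnant, the subject will be prematurely discontinued from the study". Protocol 5.4 lists it as a withdrawal criterion of its own ("The subject becomes pregnant"). Protocol 5.4.1 says that once a woman is pregnant "no additional study procedures, except an ultrasound will be conducted".

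**Window that is scored.** SAP 7.2: "Final Month is defined as the last 28 days prior to and including the Reference Day". The Reference Day is the last treatment-period visit, or the last dose date if evaluable AH data fall between that visit and that dose.

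**How an empty window is valued.** Under SAP 7.6.1.1, if there are no evaluable AH data and the UBQ reports no bleeding for the window, MBL is set to 0 mL. If the value is still missing, SAP 11.2.2.1 imputes it.

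**Related endpoints.** Suppression of bleeding (second ranked secondary, SAP 11.3.2.2) and amenorrhea (SAP 11.3.2.1) count the absence of bleeding days in the same window as success for women with at least 38 days to the Reference Day. One of the two amenorrhea summaries carries the status forward after discontinuation. The first ranked secondary, change in MBL to the Final Month, uses the same Final Month values (SAP 11.3.1).

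**The concern.** Missed menses is what pregnancy is expected to produce, and it says nothing about control of fibroid bleeding. The protocol foresees pregnancy on treatment and requires the woman to stop, but the SAP gives this event no efficacy rule. The written rules then lead to a definite classification that can be wrong.

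At stake is the meaning of a few outcomes in the primary endpoint, in the first two ranked secondaries and in amenorrhea. The planned analyses would not reveal the effect. Of the five sensitivity analyses in SAP 11.2.3, the first ignores discontinuation reasons altogether. Non-responder imputation acts only on missing MBL, whereas here MBL may be an assigned zero. The remaining three keep the same three reasons. The full analysis set in SAP 5.1 has no pregnancy exclusion, and nothing censors MBL at conception.

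**Working it through.** **1. Tracing the rules for one woman**

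- Her urine test at a monthly visit is positive, serum testing confirms it, and she is discontinued with pregnancy as the primary reason. None of the three override reasons applies.
- Her Reference Day is often that visit, since pregnancy tests are done at every visit.
- She returns no collection keg, so site staff complete the UBQ. No bleeding is recorded and the answer covers the window, so Final Month MBL = 0 mL.
- 0 < 80 mL and the reduction from baseline is 100%, so she is a responder. With at least 38 days to the Reference Day she also meets suppression and amenorrhea.

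**2. The plan's own power figure**

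Inputs (SAP 4.3 and 3.0): 200 versus 100 women, 60% versus 30%, two-sided 0.05.

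- Pooled rate = (200 × 0.60 + 100 × 0.30)/300 = 0.50
- SE under the null = √(0.25 × (1/100 + 1/200)) = 0.0612
- SE under the alternative = √(0.21/100 + 0.24/200) = 0.0574
- Power = Φ((0.30 − 1.96 × 0.0612)/0.0574) = 99.9%

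The stated figure of at least 90% is met with a wide margin. The SAP says that the safety database drives the sample size.

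**3. How many women**

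The documents give no pregnancy rate for this regimen, so the rates below are assumptions.

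- Pooled programme: 47 on-treatment pregnancies in elagolix-treated subjects (Protocol 3.2.3), over 3,417 recipients less 95 men (Protocol 3.2.2). 47/3,322 = 1.4%, which gives 2.8 in 200 women and 1.4 in 100.
- Fibroid experience: 1 on-treatment pregnancy reported in Phase 2b. With all 645 elagolix-treated women with fibroids as an approximate denominator, 1/645 = 0.16%, which gives 0.3 in 200 and 0.2 in 100.
- Stress case, chosen only as an upper bound: 3%, which gives 6 in 200 and 3 in 100.

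**4. Effect on the treatment difference**

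Start from 120/200 versus 30/100 (30.0 points). Assume every pregnant woman had been scored a responder, and rescore her as a non-responder.

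| Pregnancies, combination arm / placebo | Response after rescoring | Difference | Power |
|---|---|---|---|
| 3 / 0 | 58.5% vs 30.0% | 28.5 | 99.8% |
| 3 / 1 | 58.5% vs 29.0% | 29.5 | 99.9% |
| 6 / 0 | 57.0% vs 30.0% | 27.0 | 99.5% |
| 0 / 3 | 60.0% vs 27.0% | 33.0 | above 99.9% |

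**5. Allowing for women who would have responded anyway**

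Only would-be non-responders add false successes. Take the 1.4% rate in both arms (again an assumption) and suppose that all are scored as responders:

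- Combination arm: 2.83 × (1 − 0.60) = 1.13 women, 1.13/200 = 0.57 points. With the 79% response seen for this regimen in Phase 2b: 2.83 × 0.21 = 0.59 women, 0.30 points.
- Placebo: 1.41 × (1 − 0.30) = 0.99 women in 100, 0.99 points.
- Net, using the planned rates: 0.57 − 0.99 = −0.42 points. The difference would be slightly understated, not inflated.

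**The case against.** Three stronger readings are tempting, and the documents do not support them.

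**That pregnant women are always scored as responders.** Scoring needs AH or UBQ data that show a bleed-free or light window. Protocol 5.4.1 stops procedures other than ultrasound once a woman is pregnant, so a discontinuation-visit UBQ may not exist; MBL is then imputed and response is not automatic. A window that still holds the last menses before conception, or bleeding in early pregnancy, may fail the criteria. Women with fewer than 38 days are outside the suppression and amenorrhea analyses. The pathway through a UBQ completed at the visit with the positive test remains.

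**That response in the combination arm is inflated by a known 1.4 points.** That figure supposes that none of these women would have responded. The count of 47 also includes conceptions up to 30 days after the last dose, which cannot have affected a window that closes by then, and it pools indications, doses and exposure lengths. Protocol 3.2.2 reports ovulation in about 10% of women on this regimen, against 27% on elagolix 300 mg BID alone and 47.4% to 57.1% on lower doses, so a pooled rate probably overstates the number. Nor is the direction fixed: 20 of the 68 on-treatment pregnancies were in placebo-only subjects.

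**That automatic non-response is the only correct repair.** The listed reasons reflect failure of efficacy or tolerability. A woman whose bleeding the drug had already suppressed before she conceived would be relabelled a failure. Disregarding post-conception data is at least as defensible.

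It is also fair that the affected women will be visible: SAP 9.0 summarises discontinuation by primary reason, and SAP 12.9 summarises and lists pregnancies. That shows how many there are but does not correct their classification.

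**Conclusion.** The point holds as a minor one. The rules as written can credit pregnancy-related absence of menses as treatment success, and no population rule or sensitivity analysis removes it.

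The expected size is about 0 to 3 women in the 200-woman arm. Across 0 to 6 combination-arm and 0 to 3 placebo pregnancies, all assumed to be scored as responders, the planned 30-point difference stays between 27 and 33 points and power stays at or above 99.5%. The sign is undetermined, and neither the power nor the primary conclusion is in question. These figures rest on pregnancy rates borrowed from pooled counts and on the planned 60% and 30% response rates.

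**What to change.** State in SAP 11.2.1 and 11.3.2 that, for women whose primary discontinuation reason is pregnancy, bleeding data after the estimated conception date do not count as success. Choose one of two rules as primary and report the other as a sensitivity analysis:

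- **Add pregnancy to the non-responder list.** This follows the SAP's present approach and needs one clause. It does not repair the first ranked secondary, which is continuous.
- **Set post-conception MBL to missing and use the planned multiple imputation.** The monthly MBL values for those days must also be set to missing, because SAP 11.2.2.1 draws the Final Month value from the monthly data and would otherwise return the same zero. This also covers change in MBL to the Final Month.

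No multiple imputation is planned for suppression and amenorrhea. The simplest rule there is to count a window containing post-conception days as not achieved and to exclude these women from the amenorrhea carry-forward.

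The cost is a clause in each section and one extra sensitivity analysis, settled before unblinding. The data are already collected: pregnancy tests, discontinuation reason, and the ultrasound conception date in Protocol 6.1.6. The downside is that a few women whose bleeding was already suppressed by the drug before conception may be scored as non-responders.

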11.2.2 Primary Analysis of Primary Efficacy Endpoint

The primary analysis of the primary endpoint will be performed using the full analysis set (Section 5.1).

If a subject has missing observed Final Month MBL volume (Section 7.6), the Final Month MBL volume will be imputed using multiple imputation as described in Section 11.2.2.1.

A flow-chart showing how Final Month MBL volume will be derived is presented in Figure 2.

Figure 2. Flow-Chart for Deriving Final Month MBL Volume

11.2.2.1 Multiple Imputation

Missing Final Month MBL volume will be imputed using multiple imputation.

First, M "semi-complete" datasets of monthly MBL volume (Month 1 [Day 2 – Day 28, Month 2 [Day 29 – Day 56], Month 3 [Day 57 – Day 84], Month 4 [Day 85 – Day 112], Month 5 [Day 113 – Day 140], and Month 6 [Day 141 – Day 168]) with monotone missing data pattern will be generated via MCMC option using SAS PROC MI.¹ Then, for each of the M "semi-complete" dataset with monotone missing data, "complete" dataset of monthly MBL volume from Month 1 to Month 6 will be generated via MONOTONE REG option using SAS PROC MI. M represents the number of imputations and we set $M = 20$. The random seed 12345 will be used.

The primary analysis with multiple imputation is carried out in the following steps:

1. **Multiple Imputation:** M "complete" datasets of monthly MBL volume from Month 1 to Month 6 will be generated using SAS PROC MI as described above. The following covariates will be included in the imputation model:
 - 1) Baseline MBL volume
 - 2) Randomized treatment group
 - 3) Baseline Hemoglobin
 - 4) MBL volume in prior months
 - 5) Age of the subject at Baseline
2. **Impute Final Month MBL Volume:** In each of the M generated datasets, subject's missing Final Month MBL volume will be imputed using the MBL volume from the 'complete' dataset with Month 1 – 6 MBL volume by looking at the corresponding month of the Reference Day using analysis time window in [Table 1](#). For example, if the Reference Day of a subject is $> \text{Day } 154$, then the Month 6 MBL volume from 'complete' dataset will be used to impute Final Month MBL volume; if the Reference Day is $> \text{Day } 126$ and $\leq \text{Day } 154$, then the Month 5

MBL volume will be used to impute Final Month MBL volume and so on. Subjects whose Reference Day is the same as Study Day 1 will have their Final Month MBL volume imputed using their Month 1 MBL volume.

3. **Impute Responder Status:** The responder status (yes/no) will be derived from "complete" Final Month MBL volume, using the criteria as described in Section 11.2.1. If a subject's Final Month MBL volume is non-missing, then the observed Final Month MBL volume will be used in the analysis. If the subject prematurely discontinued due to "lack of efficacy," "requires surgery or invasive intervention for treatment of uterine fibroids," or adverse event, the subject will be considered a non-responder, regardless if the Final Month MBL is observed or missing.
4. **Analysis:** each of the M imputed datasets is analyzed separately using a logistic regression model including treatment as the main effect and Baseline MBL volume as a covariate to compare each elagolix dose group to placebo.
5. **Pooling:** estimates of the proportions of responders in each treatment group and the difference between the proportions from the M imputed datasets obtained from step 2 are combined into one overall result using PROC MIANALYZE in SAS.^{2,3}

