5.4.4 Delays in Rollover into the Extension Study

Subjects may be required to remain in the Treatment Period following the completion of the Month 6 visit if results to determine eligibility into the Extension Study are not available at the time of the Month 6 visit. Subjects will return to the study site at the same 28-day monthly visit intervals if eligibility for the extension study has not been determined before then. Subjects will continue to take study drug until eligibility has been established. These visits will be documented as and registered as Unscheduled Visits. Sites should register Unscheduled Visits in IRT in order to obtain additional kits of study drug. Procedures/assessments to be performed during the Unscheduled Visit while the subject is waiting for the determination of eligibility into the extension study, are indicated in the Table 6.

Table 6. Schedule of Assessments - Delays in Roll-Over into Extension Study

Schedule of Assessments – Delays in Roll-Over into Extension Study			
Procedure	Perform Monthly		
Symptom-directed Physical Examination	X		
Vital Signs	X		
Clinical/Safety Laboratory Tests: Hematology, Chemistry ^a	X		
Urine Pregnancy Test ^b	X		
Endocrine Panel: FSH, LH	X		
Pharmacodynamic Sample (PD): Serum Estradiol (E2) and Progesterone (P)	Х		
Contraception Counseling and Dispense Contraceptives as necessary	X		
Dispense Sanitary Products and Collection Kits (Keg, Collection Bags etc.)	Х		
Collect and Return Sanitary Products	Х		
Register Visits in IRT	Х		
Study Drug: Dispense (D) and Return (R) ^c	Х		
Study Drug Accountability	Х		
Study Drug Compliance	Х		
Adverse Event Monitoring	X		
Concomitant Medication Monitoring	Х		
Questionnaires UBQ ^d	Х		
C-SSRS – Since Last Visit	Х		
HCRU	Х		

a. Eight (8) hour minimum fast for Clinical Safety Laboratory Tests; Chemistry and Lipid Panels.

A positive urine pregnancy test result must be confirmed with a quantitative serum pregnancy test. For any subject b. who has a positive serum pregnancy test result, a TVU must be conducted as early as possible in the first trimester in order to assess the gestational age and estimated due date. The subject will be discontinued from the study at the point the pregnancy was confirmed.

[figure not shown]
Urine pregnancy test must be negative prior to providing subjects with their next monthly supply of study drug. c.

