3.0 Introduction

This statistical analysis plan (SAP) describes the planned statistical analyses for elagolix (ABT-620) Study M12-815 titled "A Phase 3 Study to Evaluate the Efficacy and Safety of Elagolix in Combination with Estradiol/Norethindrone Acetate for the Management of Heavy Menstrual Bleeding Associated with Uterine Fibroids in Premenopausal Women." The analysis plan was created based on the Study Protocol M12-815 Amendment 3 dated 25 September 2017.

This analysis plan describes both the efficacy and safety analyses. The pharmacokinetic data will be analyzed separately and is not addressed in this SAP.

The SAS System 9.2 or above will be used to perform the statistical analyses. All statistical tests will be two-sided and a significance level of 0.05 will be used unless otherwise specified.

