4.3 Sample Size

Approximately 400 subjects will be randomized in a 1:1:2 ratio to placebo (N = 100), elagolix 300 mg BID (N = 100), or elagolix 300 mg BID plus E2/NETA (N = 200). The sample size will provide at least 90% power to detect a difference between the elagolix 300 mg BID plus E2/NETA group and the placebo group in the percentage of subjects with menstrual blood loss (MBL) volume < 80 mL during the Final Month (as defined in Section 7.2) and 50% or greater reduction in MBL volume from Baseline to the Final Month under the assumption of responder rates being 60% and 30% for elagolix 300 mg BID plus E2/NETA and placebo, respectively. The sample size determination is primarily driven by the need for a sufficient number of patients for the safety database. The above sample size was calculated using nQuery advisor 7.0.

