11.2.3 Sensitivity Analyses of the Primary Efficacy Endpoint

The sensitivity analyses for the primary endpoint will use different approaches to handle prematurely discontinued subjects and missing Final Month MBL volume.

Unless otherwise specified, the analysis dataset used for sensitivity analysis is the full analysis set. Each of the following sensitivity analyses for the primary endpoint will be performed using a logistic regression model including treatment as the main effect and Baseline MBL volume as a covariate to compare each elagolix dose group to placebo.

Unless otherwise specified, subjects who prematurely discontinue study drug due to "lack of efficacy," "requires surgery or invasive intervention for treatment of uterine fibroids," or adverse events will be considered as non-responders.

1. The primary analysis will be repeated with all subjects categorized as responders/non-responders based on observed or imputed MBL volume data only (without taking into account their reasons for premature discontinuation of study drug). Multiple imputation will be performed the same way as in the primary analysis.
2. Last observation carried forward (LOCF): The primary analysis will be repeated with missing Final Month MBL volume imputed using LOCF (instead of multiple imputation) as described in Section 11.2.3.1.
3. Non-responder imputation (NRI): All subjects who have missing Final Month MBL volume will be considered as non-responders. No multiple imputation will be performed.
4. Observed cases: The primary analysis will be repeated with the observed Final Month MBL volume as defined in Section 7.6. Subjects who have missing Final Month MBL volume will be excluded from this analysis.
5. The primary analysis will be repeated using the total MBL volume collected from validated products only. All subjects will be categorized as responders/non-responders in the same manner as done in the primary analysis (i.e., using the multiple imputation described in Section 11.2.2) with exception that all AH data (including that for Baseline MBL volume) are based on the total MBL volume collected from validated products only.

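### Step 2 of the SAP's multiple imputation can fill a missing Final Month with an observed earlier month, one fixed value in all 20 datasets, for a limited set of Reference Days

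*SAP*

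**What the plan says.** - **Final Month (SAP 7.2).** "Final Month is defined as the last 28 days prior to and including the Reference Day". R is the last treatment-period visit, or the last dose if evaluable alkaline hematin (AH) data lie between the two. The window therefore moves with R.
- **What is imputed (SAP 11.2.2.1).** PROC MI completes six fixed blocks, Day 2-28 up to Day 141-168, with M = 20.
- **Step 2.** A missing Final Month takes the completed volume of the block that Table 1 pairs with R. For R after Day 154, "then the Month 6 MBL volume from 'complete' dataset will be used to impute Final Month MBL volume". For Days 127-154 it is Month 5, and so on down. There is no condition that the block be missing.
- **Observed or missing (SAP 7.6.1.1).** A window is observed if it holds any evaluable AH value, or if the Uterine Bleeding Questionnaire (UBQ) supports 0 mL.
- **Step 3.** Women whose primary reason for stopping is an adverse event, lack of efficacy or surgery are non-responders whatever their volume.
- **Treatment past Month 6.** Protocol 5.4.4 keeps women awaiting extension results in the Treatment Period: "Subjects will continue to take study drug until eligibility has been established". SAP 10.0 has an exposure category above 196 days.
- **Protocol 8.1.7.1.3.** The regression step is described as generating the Final Month volume itself.

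**The concern.** PROC MI leaves observed values alone. If the mapped block was observed and the Final Month was not, step 2 performs no imputation for that woman. It moves an earlier measurement forward and treats it as known.

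Three things are at stake. Her responder status is fixed across the 20 datasets, so she adds nothing to the between-imputation variance and the standard error is too small. The value used is not a prediction of the missing window. And the last-observation-carried-forward (LOCF) analysis, planned as sensitivity analysis 2 in SAP 11.2.3, differs little from the primary analysis for her. At R = 196 the LOCF source window is Days 141-168, exactly Month 6, so the two analyses use the same number.

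Step 2 also borrows Table 1 for bleeding data, although SAP 7.4.3 says those windows are not applied to AH or UBQ assessments.

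**Working it through.** **1. The plan's own figure.** Inputs from SAP 3.0 and 4.3: two-sided 0.05; 100 placebo and 200 combination; responder rates 30% and 60%. The claim is "The sample size will provide at least 90% power to detect a difference".

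- Pooled rate = (30 + 120)/300 = 0.50
- SE under no difference = √[0.25 × (1/100 + 1/200)] = 0.0612
- SE under the alternative = √(0.60×0.40/200 + 0.30×0.70/100) = √0.0033 = 0.0574
- Power = Φ[(0.30 − 1.96 × 0.0612)/0.0574] = 0.999

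The claim is met with much to spare. SAP 4.3 explains the excess by the safety database.

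**2. Where the two windows part.** Final Month = Day max(2, R − 27) to R. AH data after the last dose are excluded (SAP 7.4.1), so days after R cannot make the mapped month observed.

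| R | Final Month | Mapped month | Overlap (days) | Mapped days before Final Month |
|---|---|---|---|---|
| 140 | 113-140 | 113-140 | 28 | 0 |
| 150 | 123-150 | 113-140 | 18 | 10 |
| 154 | 127-154 | 113-140 | 14 | 14 |
| 160 | 133-160 | 141-168 | 20 | 0 |
| 168 | 141-168 | 141-168 | 28 | 0 |
| 174 | 147-174 | 141-168 | 22 | 6 |
| 182 | 155-182 | 141-168 | 14 | 14 |
| 196 | 169-196 | 141-168 | 0 | 28 |

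Up to Day 154 the problem needs R in 29-42, 57-70, 85-98, 113-126 or 141-154: 5 × 14 = 70 of 153 days. Day 29 is open only through a UBQ zero, because Month 1 then lies wholly inside the Final Month. On the other 83 days, and at Days 155-168, a missing Final Month implies a missing mapped month, which is truly imputed. After Day 168 every R is exposed, with no overlap from Day 196.

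**3. Examples.**

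- R = 150: products of Days 113-118 returned, bleeding of Days 141-146 not returned. The Final Month (123-150) is missing and takes the observed Month 5 volume 20 times.
- R = 40: the UBQ supports no bleeding to Day 28, then bleeding on Days 29-40 goes uncollected. Month 1 is 0 mL, so she is a responder in all 20 datasets.
- R = 200: Days 173-200 missing, Month 6 observed. Month 6 is used 20 times.

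In a toy regression imputation on simulated volumes, the SD of the filled value over 20 draws was 0 at R = 40 and R = 200. It was about 60 mL at R = 50, where the mapped month is missing.

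**4. Share of missing Final Months affected.** Assume a 28-day cycle, 6-day menses, all 28 phases equally likely, Reference Days evenly spread and earlier menses collected. With m mapped days before the Final Month (m up to 23), m of the 28 phases place a whole menses before the Final Month with at least one day in the mapped month. Another 5 phases straddle its start. A collected straddling menses makes the Final Month observed, so it must not count as affected. Lower figure: straddlers stay in the denominator (m/28). Upper figure: they leave it (m/23).

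| Reference Days | Mean m | Share |
|---|---|---|
| 164-168 | 0 | 0% |
| 169-174 | 3.5 | 12.5-15.2% |
| 43-154 | 3.75 | 13.4-16.3% |
| 141-154 | 7.5 | 26.8-32.6% |
| 180-196 | 20 | 71.4-83.1% |
| 197-224 | 28 | 100% |

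For Days 180-196 the upper figure is a direct count, 325 of 391, because m/23 fails once m exceeds 23. UBQ zeros are left out throughout.

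**5. Consequence.** The affected share f of an arm is not in the documents; 1%, 5% and 10% are assumptions.

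- If all affected combination women are fixed as responders, the rate is 0.60(1 − f) + f = 60.4%, 62% or 64%.
- Taking the lost between-imputation variance as f times the complete-data variance, the SE ratio is √[1/(1 + 1.05f)] = 0.995, 0.975 or 0.951. The SE is about 0.5%, 2.5% or 4.9% too small.
- Extreme adverse case (affected placebo women all responders, affected combination women all non-responders): power 0.998, 0.975 or 0.799.

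**The case against.** The best defence is that few women are touched. R is normally a visit date, and Months 1-5 visits fall within ±4 days of 28-day intervals (Protocol 5.1, Table 1). For R within 4 days of a Month 2-5 visit, mean m is (1+2+3+4)/9 = 1.11, giving 4-5%, so the higher early-stopper figures need off-schedule discontinuation visits. Stops for an adverse event, lack of efficacy or surgery cannot change status. For exposed early stoppers the two windows still share at least 14 days. For a held-over woman, an observed Month 6 is a sensible quantity in a 6-month trial. All of this stands and limits the size. It does not make step 2 an imputation, and the SAP does not present Month 6 as a deliberate substitute.

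A regular 28-day cycle also fits placebo better than elagolix, since Protocol 3.2.2 reports longer intervals and amenorrhea on treatment. That stands too: the shares are illustrations.

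A reader might infer that the sensitivity analyses leave these women untested. They do not. Non-responder imputation and observed cases (SAP 11.2.3, items 3 and 4) do not depend on step 2; only the LOCF contrast is weakened.

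The AH route assumes that zeros filled in between visits are not themselves evaluable AH data. The third bullet of SAP 7.6.1.1 implies this. The UBQ route does not need it.

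**Conclusion.** The point holds, within limits. As written, step 2 can insert an observed earlier volume as a constant in all 20 datasets. That departs from the multiple imputation the SAP announces and from Protocol 8.1.7.1.3. It is confined to Reference Days 1-14 days past a month end and to those after Day 168: completers at Days 169-174 and women held over for the extension.

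It is tempting to read the primary analysis as carry-forward for early stoppers in general, or as favouring elagolix. The documents support neither. On 83 of the 153 early Reference Days the mapped month is truly imputed. A carried 0 mL makes a responder, while a carried heavy month makes a non-responder.

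The shares rest on the assumed cycle and evenly spread Reference Days. The numbers of held-over women and of missing Final Months are not given, so no overall percentage of an arm can be stated. With planned power near 0.999 the primary conclusion is unlikely to change unless the affected share is large; responder rates and the standard error can shift slightly.

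**What to change.** Make the Final Month volume the variable that is imputed. Either run the imputation on 28-day windows counted back from R, or add the Final Month as the last variable in the monotone regression. In both, keep the baseline covariates and every observed earlier month as predictors.

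The first option is cleaner. In the second, most women supplying the regression have a Final Month that nearly coincides with Month 6, so the fit could reproduce Month 6 with little residual spread. That should be checked before it is adopted. The first option needs a statement of how many windows are used for women with short treatment.

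Do not set an observed mapped month to missing before PROC MI. That would discard real data, for example a fully observed Month 6 in a woman held over to Day 196.

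The cost is a short SAP revision, a small program change and a slightly larger standard error.
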